### **Suspected Adverse Reaction:**

Any AE for which there is a “reasonable possibility” that the study drug caused the AE will be regarded as a Suspected Adverse Reaction by Rigel.

“Reasonable Possibility,” for the purposes of safety reporting, means there is evidence to suggest a causal relationship between the study drug and the AE. Examples of types of evidence that would suggest a causal relationship between the study drug and the AE are:

- A single occurrence of an event that is uncommon and known to be strongly associated with study drug exposure (e.g., angioedema, blood dyscrasias, rhabdomyolysis, hepatic injury, anaphylaxis, and Stevens-Johnson syndrome);
- One or more occurrences of an event that is not commonly associated with study drug exposure but is otherwise uncommon in the population exposed to the study drug (e.g., tendon rupture or heart valve lesions in young adults or intussusception in healthy infants). If the event occurs in association with other factors strongly suggesting causation (e.g., strong temporal association, event recurs on rechallenge), a single case may be sufficiently persuasive; but often, more than 1 occurrence (from 1 or multiple studies) would be needed before the Sponsor could make a determination of whether the study drug caused the event; or
- An aggregate analysis of specific events that can be anticipated to occur in the study population independent of study drug exposure. Such events include known consequences of the underlying disease or condition under investigation (e.g., symptoms, disease progression) or events unlikely to be related to the underlying disease or condition under investigation but commonly occur in the study population independent of drug therapy (e.g., cardiovascular events in an elderly population). An aggregate analysis (across studies) will identify those events that occur more frequently in the study drug treatment group than in a concurrent or historical control group.

This definition of *suspected adverse reaction* and the application of the *reasonable possibility* causality standard are considered to be consistent with the concepts and discussion about causality in the International Conference on Harmonisation (ICH) E2A guidance.

**Unexpected:** An AE that is not listed in the Investigator’s Brochure or is not listed at the specificity or severity that has been observed will be regarded as “unexpected”. For example, hepatic necrosis would be “unexpected” (by virtue of greater severity) if the Investigator’s Brochure referred only to elevated hepatic enzymes or hepatitis. Similarly, cerebral thromboembolism and cerebral vasculitis would be “unexpected” (by virtue of greater specificity) if the Investigator’s Brochure listed only cerebral vascular accidents. “Unexpected”

also refers to AEs that are mentioned in the Investigator's Brochure as occurring with a class of drugs or as anticipated from the pharmacological properties of the study drug but are not specifically mentioned as occurring with the study drug under investigation.

**Causality:** The investigator is to assess the causal relation (e.g., whether there is a reasonable possibility that the study drug caused the event) using the following definitions:

- **Definitely Related:** A reaction that has reasonable evidence showing a direct causal relationship;
- **Probable:** A reaction that follows a reasonable temporal sequence from administration of the investigational study drug or its class of drugs; that follows a known or expected response pattern to the suspected investigational study drug; and that could not be reasonably explained by the known characteristics of that subject's clinical state or the background rate for the event in the population being studied;
- **Possible:** A reaction that follows a reasonable temporal sequence from administration; that follows a known or expected response pattern to the suspected investigational study drug; but that could readily have been produced by a number of other factors;
- **Unlikely:** A reaction that does not follow a reasonable temporal sequence from administration, or there is a reasonably compelling alternative explanation; however, causation by the investigational study drug cannot be ruled out; and
- **Not Related:** A reaction that does not have any reasonable suspected causal relationship.

If the relationship of an adverse event to study drug is determined to be definitely related, probable, or possible, then the relationship assigned for the purposes of regulatory reporting will be "yes."

If the relationship of an adverse event to study drug is determined to be unlikely or not related, then the relationship assigned for the purposes of regulatory reporting will be "no."

## 9.2 Documenting and Reporting of Adverse Events and Serious Adverse Events by Investigators

The Investigator is responsible for ensuring that all AEs (including SAEs) that are observed or reported during the study, as outlined in the prior sections, are recorded on the eCRF with the exception of screen failures. The Investigator is not required to record screen failure AE/SAEs on the eCRF. These are recorded on an SAE Form and submitted to Drug Safety only per the expedited reporting process for SAEs (see [Section 9.2.3](#)).

### 9.2.1 Adverse Event Reporting Period

The AE reporting period begins with the signing of the initial informed consent form (or the first informed consent form if more than one informed consent is signed due to rescreening) and ends with the final study (follow-up) visit.

If an AE or SAE is present at the withdrawal visit or at the subject's last participation in the study, it should be followed until time of resolution or stabilized unless the subjects is lost to follow up. Resolution means the subject has returned to baseline state of health or the investigator does not expect any further improvement or worsening of the event.

Any SAE occurring within 14 days of the last dose of study drug should be reported.

In case of ongoing SAEs at the time of database closure, the data obtained at the time of database closure will be used in the statistical analysis. The follow-up of the SAE will be documented in the source documents and will be described in the final report or as an addendum, as appropriate.

### **9.2.2 Assessment of Adverse Events**

Investigators will assess the occurrence of AEs and SAEs at all subject evaluation time points during the study. All AEs and SAEs, whether volunteered by the subject, discovered by study staff during questioning, or detected through PE, clinically significant laboratory test, or other means, will be recorded in the subject's medical record and on the AE eCRF and, when applicable, on an SAE form.

Each recorded AE or SAE will be described by its duration (e.g., start and end dates), severity, regulatory seriousness criteria, if applicable, suspected relationship to the investigational product (see guidance above), and any actions taken.

All deaths should be reported with the primary cause of death as the AE term, as death is typically the outcome of the event, not the event itself. The primary cause of death on the autopsy report should be the term reported. Autopsy and postmortem reports must be forwarded to Rigel, or designee, as described below.

If study drug is discontinued because of an SAE, this information must be included in the SAE report.

### **9.2.3 Expedited Reporting Requirements for Serious Adverse Events**

An investigator should report a SAE within 24 hours of his/her awareness of the event by completing and sending the provided SAE form to Rigel's authorized safety representative. Additionally, all fatal or life-threatening SAEs should be telephoned to the Medical Monitor as soon as the investigator learns of the event.

The SAE form should be sent to the following email or fax:

**Email:** [[contact]](mailto:[contact])

**[contact]

The site may contact Rigel Drug Safety at the above fax/e-mail with questions regarding reporting of SAEs.

Reporting of SUSARs will be in accordance with Directive 2001/20/EC or as per national regulatory requirements in participating countries.

### 9.3 Reporting of Serious Adverse Events by Sponsor

Regulatory Authorities, IRBs/IECs, and Principal Investigators will be notified of SAEs in accordance with applicable requirements (e.g., GCPs, ICH guidelines, national regulations, and local requirements). The country-specific requirements, timelines, and processes for complying with these requirements are described in detail in the Study Operations Manual and/or Safety Plan.

For the purposes of expedited regulatory reporting, only those SAEs that are assessed as Suspected Adverse Reactions and unexpected per the Investigator's Brochure will be unblinded by a Rigel Safety representative or designee. All other study personnel, including clinical sites and investigators shall remain blinded to the unblinded subject's treatment assignment.

Rigel's Safety Surveillance Committee will review and evaluate accumulating safety data from the entire clinical trial database for the study drug at appropriate intervals (e.g., quarterly) to identify new safety signals or increased frequency of events. This will include an aggregate review and comparison to the control group of SAEs that were deemed as "not suspected" as being associated with use of the study drug.

### 9.4 Pregnancy

Although pregnancy itself is not regarded as an AE, the initial notification and outcome of any pregnancy that occurs during the study must be documented. The pregnancy in a female study participant and the pregnancy outcome must be reported to Rigel Drug Safety within 24 hours of awareness as outlined in [Section 9.2.3](#), using an SAE form and the applicable pregnancy form (i.e. Exposure in Utero Form – Part I or Exposure in Utero Follow-up Form – Part II). Partners that become pregnant by a male subject do not need to report pregnancy.

Prior to screening, females of childbearing potential must agree in the ICF to take appropriate measures to avoid pregnancy at all times during the study, commencing from the time of consent to 30 days after the last dose of study drug, and, if pregnancy occurs, they must agree to report the pregnancy and cooperate with the investigator as set forth below.

Should a pregnancy occur, the female study participant must immediately inform the investigator and must immediately discontinue study drug. The investigator should counsel the study participant on any risks of continuing the pregnancy and any possible effects on the fetus in view of the subject's participation in the study. The study participant must agree to follow-up by the investigator regarding the outcome of any pregnancy that occurs during the study. Outcome is defined as elective termination of the pregnancy, miscarriage, or delivery of the fetus. For pregnancies with an outcome of live birth, the newborn infant will be followed by the investigator until it is 30 days old. Any congenital anomaly/birth defect noted in the infant must be reported as an SAE.

The investigator will notify Rigel or its authorized representative of a pregnancy occurring in a female study participant within 24 hours of first becoming aware of such pregnancy using the pregnancy notification form. All follow-up information gathered by the investigator shall be reported to the Sponsor within 24 hours of investigator's first knowledge of such information using the pregnancy exposure form.

## 9.5 Special Situation Events

Other events that may or may not be associated with an AE/SAE or regarded as such are considered “Special Situation Events” and are reportable to Rigel Drug Safety within 24 hours of awareness. These are events of medication error, overdose, misuse, abuse, or inadvertent or accidental drug exposure.

- Medication error: an unintentional error in the prescribing, dispensing, or administration of the study drug
- Overdose: there is an AE associated with the overdose OR the dose or dosage regimen administered significantly exceeds the weekly prescribed dose in the judgment of the medical monitor.
- Misuse: intentional and inappropriate use of study drug not in accordance with study drug administration instructions
- Abuse: intentional and excessive use of study drug, either persistent or sporadic
- Inadvertent or accidental exposure: unintended exposure to study drug that may result in noxious and/or harmful consequences to the person who is exposed

In addition, the Investigator should notify the Medical Monitor if a subject meets Hy’s Law criteria 1 and 2 to confirm whether an event meets all three of the criteria for Hy’s Law, as shown below:

1. Aspartate aminotransferase (AST) or alanine aminotransferase (ALT)  $\geq 3x$  upper limit of normal (ULN).
2. Total bilirubin (total BL)  $>2x$  ULN and alkaline phosphatase (ALP)  $<2x$  ULN.
3. No other reason can be found to explain the combination of increased ALT and total BL, such as viral hepatitis A, B, or C; preexisting or acute liver disease; or another drug capable of causing the observed injury.

Any confirmed cases of Hy’s law should be reported per the requirements in [Section 9.2.3](#).

## 10.0 DATA ANALYSIS AND STATISTICAL METHODS

This section provides the key details of the statistical analyses to be performed using data captured according to this protocol. A complete statistical analysis plan (SAP) describing all planned analyses will be finalized prior to database lock.

### 10.1 Determination of Sample Size

The sample size is based on the number of subjects necessary to demonstrate efficacy in the primary endpoint: achievement of durable hemoglobin response (Yes/No).

#### Sample Size for Primary Endpoint: Achievement of durable hemoglobin response

In a previous phase 2 study, the efficacy of 12 to 24 weeks of treatment with fostamatinib in subjects with wAIHA who had failed at least one prior treatment regimen was evaluated. Approximately 27% (7 out of 26) of subjects treated with fostamatinib achieved a durable response, defined as a hemoglobin level above 10 g/dL with at least 2 g/dL higher than the baseline hemoglobin, not attributable to RBC transfusion or other rescue treatments on at least 3 scheduled visits within 24 weeks of treatment. No data are available on placebo response rates for this population. It is expected that no more than approximately 5% of placebo subjects would achieve a durable hemoglobin response.

Under these assumptions, a sample size of 90 subjects (i.e., 45 subjects per treatment group) will yield at least 84% power to detect a difference between the 2 groups at the 0.05 two-sided significance level using Fisher's exact test.

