### 3.4 Efficacy in wAIHA

A Phase 2 multi-center, open-label, Simon two-stage study (C788-053) in adults with AIHA who have failed at least one prior treatment regimen was conducted at sites in the US and Canada. Patients were treated for 24 weeks with fostamatinib 150 mg bid. Seventeen patients were to be enrolled initially in Stage 1. If at least 4 patients achieved a hemoglobin response (defined as hemoglobin >10 g/dL and  $\geq 2$  g/dL higher than baseline) by Week 24, up to 20 additional patients were to be enrolled in Stage 2 for a total of up to 37 patients. The protocol allowed up to two thirds of patients with secondary AIHA.

At the time of data cutoff for an interim analysis, a total of 19 patients with AIHA received fostamatinib in Stage 1, 17 of whom were evaluable for efficacy. Eight of the 17 patients (47%) achieved a hemoglobin response by Week 24, meeting the criteria for initiating Stage 2; a ninth subject achieved a hemoglobin response by Week 30. The extension study is ongoing. Enrollment in the Phase 2 study was halted in Aug 2018 after a decision was made to initiate a Phase 3 study in wAIHA.

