#### 4.2 Primary Efficacy Endpoint

The primary efficacy endpoint is achievement of durable hemoglobin response (Yes/No) defined as achieving a hemoglobin level  $\geq 10$  g/dL with an increase from Baseline in hemoglobin level of  $\geq 2$  g/dL on 3 consecutive available visits during the 24-week treatment period, in which hemoglobin measurements eligible for this definition occurred outside a Rescue Treatment Visit Exclusion Period (see [Section 10.3.6](#)).

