### **10.3.6 Analysis of Primary Efficacy Endpoint**

The primary efficacy endpoint is achievement of durable hemoglobin response (Yes/No) defined as achieving a hemoglobin level  $\geq 10$  g/dL with an increase from Baseline in hemoglobin level of  $\geq 2$  g/dL on 3 consecutive available visits during the 24-week treatment period, in which hemoglobin measurements eligible for this definition occurred outside a Rescue Treatment Visit Exclusion Period.

Available visits are defined as any scheduled visit where a plasma sample was collected, and hemoglobin level analyzed using either central or local laboratory.

For permitted rescue medications, a Rescue Treatment Visit Exclusion Period begins with the initiation of the rescue medication. The end of a Rescue Treatment Visit Exclusion Period is 4 weeks (28 days) following the return of steroid use to Baseline level or the last administration of rescue medication, whichever event occurs the latest. Any hemoglobin measurements made during this exclusion period are not eligible for any endpoint definition.

For non-permitted rescue medications, a Rescue Treatment Visit Exclusion Period begins with the initiation of the rescue medication and ends at Week 24/Week 26 or date of early termination from study.

If durable hemoglobin response cannot be determined because the subject discontinued from the study prior to attaining a durable response, then the subject will be assumed as not having achieved a durable response.

Analysis will be performed after all randomized subjects have completed the 24 weeks of treatment or discontinued from the study. All subjects randomized will be included in the analysis (ITT population). The following hypothesis will be evaluated:

$$H_0: \Theta_{\text{Fostamatinib,Placebo}} = 1$$

$$H_a: \Theta_{\text{Fostamatinib,Placebo}} \neq 1,$$

where  $\Theta_{\text{Fostamatinib,Placebo}}$  is the odds ratio of durable hemoglobin response due to treatment.

Analysis will be performed using Cochran-Mantel-Haenszel (CMH) test stratified by concomitant steroid use at Baseline ( $\geq 20$  vs.  $< 20$  mg daily), and screening hemoglobin level ( $< 9$  vs.  $\geq 9$  g/dL). The odds ratio will be presented along with the 95% CI. The study will be considered to meet its primary efficacy objective if the lower bound of the 95% CI of the odds ratio of durable hemoglobin response between the Fostamatinib and Placebo-treated subjects is greater than 1.

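### The 27% used to size the trial was scored on at least 3 visits, with no stated consecutive requirement, but the primary endpoint needs 3 consecutive visits; re-score Phase 2 and restate the power

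*Combined protocol and SAP*

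**What the plan says.** Section 10.1 bases the sample size on the primary endpoint and takes the active-arm rate from Phase 2: "Approximately 27% (7 out of 26) of subjects treated with fostamatinib achieved a durable response". For the Phase 2 response it gives a threshold, namely "a hemoglobin level above 10 g/dL with at least 2 g/dL higher than the baseline hemoglobin". Its rule on rescue and visits is that the response had to be "not attributable to RBC transfusion or other rescue treatments on at least 3 scheduled visits within 24 weeks of treatment". The synopsis repeats the 27% without that definition.

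Sections 4.2 and 10.3.6 (and the synopsis) define the Phase 3 primary endpoint as hemoglobin of at least 10 g/dL with a rise of at least 2 g/dL "on 3 consecutive available visits during the 24-week treatment period". Section 10.3.6 adds two rules:

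- Which visits count: "Available visits are defined as any scheduled visit where a plasma sample was collected" and hemoglobin was measured, by a central or local laboratory.
- Rescue: after permitted rescue, values are ineligible from the start of rescue until 28 days after the last rescue dose or the return of steroids to the baseline level, whichever is later.

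From 27% on fostamatinib, no more than about 5% on placebo and 45 subjects per arm, Section 10.1 states at least 84% power by Fisher's exact test at two-sided 0.05. It does not mention that the two responder definitions differ.

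**The concern.** Both studies call the outcome durable response, but the visit rules differ. A subject with three qualifying visits separated by non-qualifying ones satisfies the Phase 2 rule as Section 10.1 words it, and does not satisfy the Phase 3 rule. If any of the 7 Phase 2 responders had that pattern, 7/26 overstates what the same data would give under the endpoint being tested.

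What is at stake is the planning assumption. The power statement is only as good as the rate put into it, and with an expected placebo rate near 5% it is sensitive to one or two Phase 2 responders. Type I error, the validity of the endpoint and the primary analysis are not affected.

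**Working it through.** **1. The two definitions side by side**

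| Feature | Phase 2 (Section 10.1) | Phase 3 (Sections 4.2, 10.3.6) | Likely effect on the Phase 3 rate |
|---|---|---|---|
| Visit pattern | At least 3 scheduled visits; consecutive not mentioned | 3 consecutive available visits | Same or lower |
| Threshold | Above 10 g/dL | 10 g/dL or more | Same or higher |
| Missed visits | Not stated | Not counted, so they do not break a run | Higher than if a missed visit broke the run |
| Rescue | Not attributable to rescue | Fixed exclusion with 28-day washout | Plausibly lower |
| Treatment length | 12 to 24 weeks (24 weeks in Section 3.4) | 24 weeks planned | Higher, if some Phase 2 subjects had less time |
| Regimen | 150 mg bid (Section 3.4) | 100 mg bid, increased from Week 4 if tolerated | Cannot be determined |
| Visit frequency | Not given | Every 2 weeks (Table 4) | Cannot be determined |

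For the first row the direction is certain. On the same visits, with everything else equal, a subject with 3 consecutive qualifying visits also has at least 3. Consecutive-rule responders are therefore a subset of the others, and the count of 7 can only stay or fall.

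**2. The plan's own figure**

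Power = Σₐ Σ_b Bin(a; 45, p₁) · Bin(b; 45, p₂) · 1[Fisher two-sided p(a, b) ≤ 0.05], summed over all tables with 45 per arm. The two-sided p-value is the sum of the hypergeometric probabilities no larger than that of the observed table.

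With p₁ = 0.27 and p₂ = 0.05 this gives 78.0% (77.7% at exactly 7/26), against the stated 84%. The normal approximation gives 82.4% with pooled variance and 84.7% with unpooled variance. Fisher reaches 84.1% at 27% if placebo is 4%. How the 84% was computed is a separate question. The same Fisher calculation is used throughout below, so the comparisons do not depend on it.

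**3. Sensitivity to the visit rule**

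The documents do not give the Phase 2 rate under the consecutive rule. Assumption: 0, 1 or 2 of the 7 responders lack a consecutive run. Since a stricter rule could also lower the placebo rate, and 5% is itself given as an upper figure without data, placebo rates of 5%, 4% and 3% are shown.

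| Phase 2 rate after re-scoring | Placebo 5% | Placebo 4% | Placebo 3% |
|---|---|---|---|
| 7/26 = 26.9% | 77.7% | 83.9% | 89.3% |
| 6/26 = 23.1% | 62.8% | 70.7% | 78.2% |
| 5/26 = 19.2% | 44.1% | 52.2% | 60.8% |

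At 5% placebo, losing one responder costs 77.7 − 62.8 = 14.9 points, and losing two costs 77.7 − 44.1 = 33.6 points. The subjects per arm needed for 84% Fisher power against 5% are 52 at 27%, 68 at 23.1% and 98 at 19.2%.

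**4. Precision of the input**

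The exact 95% interval for 7/26 runs from the 2.5% quantile of Beta(7, 20) to the 97.5% quantile of Beta(8, 19): 11.6% to 47.8%.

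**The case against.** Four points can be made for the plan.

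- **The loss may be zero.** Section 10.1 gives a one-sentence summary of another study. It does not say that non-consecutive visits were used or that any responder lacked a run. A reader might infer that Phase 2 counted visits in any order. The text only fails to say consecutive, and the Phase 2 protocol and visit schedule are not in the documents. This stands: all 7 may meet both rules.
- **Other differences can raise the rate.** A reader might infer that 27% is a ceiling for the Phase 3 endpoint. It is not. The threshold is slightly easier, some Phase 2 subjects may have been treated for as little as 12 weeks ("the efficacy of 12 to 24 weeks of treatment with fostamatinib"), missed visits do not break a run, and the interval for 7/26 reaches 47.8%. This stands in full.
- **The placebo rate may fall too.** This stands in part. At 6/26, power recovers from 63% to 78% if placebo is 3%, and at 5/26 from 44% to 61%. Both remain below 84%.
- **Looser measures are already planned.** A reader might infer that a failed trial could not be told apart from the effect of a stricter definition. That goes too far. Section 4.3 includes response on at least one visit and a rise of at least 2 g/dL. Section 4.5 includes the percentage of visits with response and the total duration of response. These would show intermittent response, although none is the Phase 2 responder rate itself.

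The lower starting dose adds little. Section 5.4 explains it and returns tolerating subjects to the Phase 2 dose from Week 4. Its effect on the response rate cannot be judged from the documents.

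None of this removes the mismatch. With differences acting in both directions, the value of 27% for this endpoint cannot be known without re-scoring.

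**Conclusion.** The point holds in a limited form. The expected active rate comes from a criterion that is looser in its visit pattern than the primary endpoint, and the plan neither adjusts for this nor mentions it. On that feature alone 27% is either right or optimistic. Over all features the net direction is unknown, so the documents do not support reading 27% as an upper limit.

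The possible size is large for a small change in the input. Against 5% on placebo, Fisher power is 78%, 63% or 44% if 0, 1 or 2 of the 7 responders are lost; against 3% it is 89%, 78% or 61%. These figures assume 45 per arm, two-sided 0.05 and a true rate equal to the re-scored Phase 2 proportion. The number lost is an assumption, and zero is possible.

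This is a defect in the sample-size justification. It should be corrected, but it does not undermine the primary analysis.

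**What to change.** 1. Re-score the 26 Phase 2 subjects by the rule in Sections 4.2 and 10.3.6: 3 consecutive available visits, at least 10 g/dL, a rise of at least 2 g/dL, and the rescue exclusion period.
2. Put that rate in Section 10.1 and the synopsis, and restate the power from it. If re-scoring is not possible, say that 27% comes from a different definition and show power over a range of active and placebo rates, as in the second table above.
3. Reconcile the Phase 2 treatment length between Section 10.1 (12 to 24 weeks) and Section 3.4 ("Patients were treated for 24 weeks with fostamatinib 150 mg bid").
4. Optional: add a supportive Phase 3 responder analysis by the Phase 2 definition, so that the two studies can be compared. Section 10.0 finalizes the SAP before database lock, so this can still be pre-specified.

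The cost is a re-derivation from the earlier study's data, a text change and at most one extra table. It needs no new patients and no change to the primary test. The downside is that the stated rate and power may become less favourable.

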**Statistical Methods:**

Determination of Sample Size:

The sample size is based on the number of subjects necessary to demonstrate efficacy in the primary endpoint: achievement of durable hemoglobin response (Yes/No). In a previous phase 2 study, approximately 27% of subjects (7 out of 26) treated with fostamatinib achieved a durable response.

No data are available on placebo response rates for this population. It is expected that no more than approximately 5% of placebo subjects would achieve a durable hemoglobin response. Under these assumptions, a sample size of 90 subjects (i.e., 45 subjects per treatment group)

will yield at least 84% power to detect a difference between the 2 groups at the 0.05 two-sided significance level using Fisher's exact test.

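### The stated power of at least 84% is wrong for the test and inputs given: Fisher's exact test with 45 per group, 27% vs 5%, has 78.0% power

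*Combined protocol and SAP*

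**What the plan says.** Section 10.1 bases the sample size on durable hemoglobin response and supplies every input to the calculation: 27% (7 of 26) on fostamatinib from Phase 2, about 5% at most on placebo (with the remark that no placebo data exist), and 90 subjects split 45 and 45. It concludes that this "will yield at least 84% power to detect a difference between the 2 groups at the 0.05 two-sided significance level using Fisher's exact test". The synopsis repeats the claim: "will yield at least 84% power to detect a difference between the 2 groups".

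Two other places bear on the figure.

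- Section 10.3.6 names a stratified Cochran-Mantel-Haenszel (CMH) test and then sets the success rule: "The study will be considered to meet its primary efficacy objective if the lower bound of the 95% CI of the odds ratio" for fostamatinib against placebo is above 1.
- The Phase 2 response behind the 27% was "defined as a hemoglobin level above 10 g/dL with at least 2 g/dL higher than the baseline hemoglobin", not due to transfusion or other rescue, "on at least 3 scheduled visits within 24 weeks of treatment". The Phase 3 endpoint in section 4.2 needs a level of at least 10 g/dL with a rise of at least 2 g/dL "on 3 consecutive available visits during the 24-week treatment period", outside a rescue exclusion period.

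**The concern.** The power sentence is complete: it names the test, the sidedness, the alpha, the group size and both rates. It can therefore be checked directly, and it should reproduce to within rounding. Fisher's test is conservative at small event counts (about 2 placebo responders expected, 45 × 0.05 = 2.25), so a figure of 84% looked too high.

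This sentence is the only justification given for 90 subjects. If it is wrong, readers of the protocol take the chance of missing the assumed effect to be at most 16% when, under the plan's own test and rates, it is larger. The test named for power is also not the rule that decides the trial, so the stated figure describes neither.

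**Working it through.** **Inputs** (section 10.1): p1 = 0.27 (or 7/26 = 0.269), p2 = 0.05, n = 45 per group, two-sided alpha 0.05, Fisher's exact test. No dropout inflation is stated. Under section 10.3.6, subjects who discontinue before a durable response count as non-responders.

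**Trying to reproduce 84%.** Normal approximation with unpooled variance:

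- SE = √[(0.27×0.73 + 0.05×0.95)/45] = √(0.2446/45) = 0.0737
- z = 0.22/0.0737 − 1.96 = 1.024, so power = Φ(1.024) = 84.7%

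With pooled variance under the null (mean rate 0.16):

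- SE0 = √(2×0.16×0.84/45) = 0.0773
- z = (0.22 − 1.96×0.0773)/0.0737 = 0.929, so power = 82.4%

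Mid-P Fisher gives 83.3%. The stated figure is thus near methods that the plan does not name. The unpooled approximation is a plausible source, but that is an inference.

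**Fisher's exact test as named.** Power = Σ over all 46 × 46 outcomes (x, y) of Bin(x; 45, 0.27) × Bin(y; 45, 0.05), counting outcomes with two-sided Fisher p ≤ 0.05. For each placebo count y there is a smallest significant fostamatinib count x:

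| Placebo responders y | P(y) at 5% | Smallest significant x (p) | P(X ≥ x) at 27% | Contribution | Running total |
|---|---|---|---|---|---|
| 0 | 0.0994 | 6 (0.026) | 0.9914 | 0.0986 | 0.0986 |
| 1 | 0.2355 | 8 (0.030) | 0.9463 | 0.2229 | 0.3215 |
| 2 | 0.2727 | 9 (0.0496) | 0.8929 | 0.2435 | 0.5650 |
| 3 | 0.2057 | 11 (0.039) | 0.7037 | 0.1448 | 0.7097 |
| 4 | 0.1137 | 13 (0.029) | 0.4432 | 0.0504 | 0.7601 |
| 5 | 0.0491 | 14 (0.037) | 0.3180 | 0.0156 | 0.7757 |
| 6 | 0.0172 | 15 (0.045) | 0.2122 | 0.0037 | 0.7794 |
| 7 and 8 | 0.0063 | 17, 18 | 0.0753, 0.0399 | 0.0004 | 0.7798 |

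Rejections in the wrong direction are negligible. Power is **0.7798**, or 0.7773 with 7/26. Defining the two-sided p-value by doubling the one-sided value gives the same answer.

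**What would make 84% true for Fisher's test**

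- At 45 per group: placebo 4.0% with fostamatinib 27%, or fostamatinib 29.1% with placebo 5%.
- At 27% vs 5%: 52 per group (84.1%); 51 per group gives 83.1%.
- Rounding is not enough: 27.49% vs 4.51% gives 82.5%.

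**The rule that decides the trial.** Section 10.3.6 does not name the odds-ratio interval method or say what happens with zero placebo responders, which has probability 0.95^45 = 9.9% at a 5% rate. The figures below therefore rest on assumed methods. For a single stratum with a Wald interval on the log odds ratio, at 27% vs 5%:

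- zero-placebo results count as failures: 72.7%
- 0.5 added to every cell: 79.7%
- zero-placebo results judged by the uncorrected CMH test: 82.6%

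In simulations with four strata (200,000 trials; stratum sizes assumed; equal rates in every stratum), the Mantel-Haenszel odds ratio with the Robins-Breslow-Greenland interval gave 72.2–72.4% when an undefined interval is a failure and 82.2–82.4% when it is judged by CMH. The uncorrected CMH p-value alone gives 86.2% for one stratum and 85.7–86.0% stratified. That is the power of a different rule.

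**Sensitivity to the 27%.** The Phase 2 definition asks for a level above 10 g/dL on at least 3 scheduled visits; the Phase 3 definition asks for 10 g/dL or more on 3 consecutive available visits. Neither contains the other, so the direction of any change is unknown. Fisher power at hypothetical recounts against 5%: 5/26 gives 44%, 6/26 gives 63%, 8/26 gives 88%.

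**The case against.** The strongest reply is that the planned test is CMH, not Fisher's. At the same inputs the uncorrected CMH p-value has about 86% power, so naming Fisher's test could be seen as a slip in a descriptive sentence that changes no rule. This stands in part: the error does not show that 90 subjects are too few under the planned analysis. It does not rescue the sentence, which names Fisher's test, and the CMH p-value is not the stated success criterion. None of the odds-ratio interval versions tried reaches 84%.

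A second reply is that the placebo rate is given as an upper limit, and Fisher's test does have 84.1% power at 4% and 89.4% at 3%. That is true, and the stated figure holds over much of the assumed range. But a claim of at least 84% has to hold at the limit of 5%, where power is lowest.

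Third, the protocol defers full analysis detail to an SAP to be finalised before database lock, so the interval method and zero-cell handling may be set there. That is fair. The interval-rule powers depend on assumed conventions and do not replace the stated number. The Phase 2 recounts are likewise hypothetical, and section 10.1 discloses the Phase 2 definition openly. Both are side points, and the main point does not depend on them. The plan also sets no 80% threshold of its own.

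**Conclusion.** The concern holds. Under the plan's own test, alpha, group size and rates, power is 78.0% (77.7% with 7/26) against a stated minimum of 84%. The type II error is 22% where at most 16% is implied. This result uses only figures in section 10.1 and is exact; no convention for the two-sided p-value or rounding of the rates brings it to 84%.

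The conclusion is limited to the stated figure and its basis. Power under the odds-ratio interval rule runs from about 72% to 83% depending on assumptions that the documents do not settle. The effect of the changed response definition on the 27% is unknown. It must be fixed because the sentence is wrong as written and is the sole stated justification for the sample size.

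**What to change.** In section 10.1 and in the synopsis, replace the power statement with approximately 78% for Fisher's exact test at 27% vs 5%, 45 per group, two-sided 0.05. Alternatively, give the power of the section 10.3.6 rule, and state with it the odds-ratio interval method and the handling of zero placebo responders. The 86% CMH p-value figure should not be quoted as the power of that rule.

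As a useful addition, recount the 26 Phase 2 subjects under the Phase 3 definition and report power at that rate. The core correction does not depend on this.

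The cost is one sentence in each of two places, plus the recount of existing data if it is done. The stated power becomes less favourable. Sample size, endpoint and visits do not change.
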